10.2.5 SAEs (Including Deaths) and Adverse Events Leading to Study Drug Discontinuation

Treatment-emergent SAEs (including deaths) and AEs leading to discontinuation of study drug will be summarized by SOC and PT and in listing format.

A listing of pre-treatment SAEs with onset dates prior to the first dose of study drug will be provided.

10.2.6 Safety Topics of Interest

Safety Topics of Interest (STI) will be summarized according to the search criteria are provided in [Appendix B](#).

The final list will be based on the most updated final version of risankizumab Product Safety Statistical Analysis Plan, which is consistent to the most updated risankizumab Risk Management Plan.

Listings of selected Areas of safety interest will also be provided.

10.3 Analysis of Laboratory Data

Data collected from central and local laboratories, including additional laboratory testing due to an SAE, will be used in all analyses, except for Baseline where SAE-related laboratory assessments on or before the first dose of study drug will be excluded. The clinical laboratory tests defined in the protocol operations manual (e.g., hematology and clinical chemistry) will be summarized.

Mean change from Baseline to each applicable post-baseline visit will be summarized for selected laboratory variables among the Safety_A, Safety_B_R, Safety_B_NR, and Safety_LT Populations. The following descriptive statistics will be presented by treatment groups: number of observations, Baseline mean, visit mean, mean change from Baseline and its standard error, and the 95% confidence interval of the mean change from Baseline.

In addition, laboratory parameters will be tabulated using shift tables from Baseline to minimum and maximum values among Safety_A, Safety_B_R and Safety_B_NR, and Safety_LT Populations categorized by the toxicity grade according to NCI CTCAE Version 4.03¹ of the laboratory used for each sample. A similar shift table will also be provided to summarize shifts from Baseline to the final post-baseline value in each period.

Laboratory abnormalities meeting CTC criteria grade 3 and 4 will be summarized among all safety populations.

Laboratory abnormalities will be evaluated based on Potentially Clinically Important (PCI) criteria ([Appendix C](#)). For each laboratory PCI criterion, the number and percentage of subjects who have a laboratory value meeting the criteria will be summarized. Listings will be provided to summarize subject-level laboratory data for subjects meeting PCI criteria.

In addition, the frequencies and percentages of subjects with post baseline liver specific function test values in ALT/SGPT, AST/SGOT, alkaline phosphatase, and total bilirubin will be categorized as follows:

- ALT > 3.0 × ULN
- ALT > 5.0 × ULN
- ALT > 10.0 × ULN
- ALT > 20.0 × ULN
- AST > 3.0 × ULN
- AST > 5.0 × ULN
- AST > 10.0 × ULN
- AST > 20.0 × ULN
- Alkaline phosphatase > 1.5 × ULN
- Total bilirubin > 1.5 × ULN
- Total bilirubin > 2.0 × ULN
- ALT and/or AST > 3× ULN and Total bilirubin > 1.5× ULN
- ALT and/or AST > 3× ULN and Total bilirubin > 2× ULN
- ALT > 3× ULN and Total bilirubin > 1.5× ULN
- ALT > 3× ULN and Total bilirubin > 2× ULN

The listing will include all subjects who met any of the following four criteria:

- ALT > 3 × ULN, or
- AST > 3 × ULN, or
- ALP > 1.5 × ULN, or
- Total bilirubin > 1.5 × ULN.

A listing of possible Hy's Law cases, defined as those who meet all of the following conditions will be provided.

- ALT of $> 3 \times \text{ULN}$ or AST of $> 3 \times \text{ULN}$
- Total bilirubin $\geq 2 \times \text{ULN}$

Urinalysis and pregnancy testing results will be provided in listings only.

10.4 Analysis of Vital Signs

Vital sign measurements of systolic and diastolic blood pressure will be summarized.

Change from baseline to each applicable post-baseline visit will be summarized for each vital sign variable among the Safety_A, Safety_B_R, Safety_B_NR, and Safety_LT Populations. The following descriptive statistics will be presented by treatment groups: number of observations, Baseline mean, visit mean, mean change from Baseline and its standard error, and the 95% confidence interval of the mean change from Baseline.

Vital sign variables will be evaluated based on potentially clinically important (PCI) criteria ([Appendix C](#)) among all safety populations. For each vital sign PCI criterion, the number and percentage of subjects who have a vital sign value meeting the criteria at least once in each period will be summarized. Listings will be provided to summarize subject-level vital sign data for subjects meeting PCI criteria.

10.5 Safety Subgroup Analyses

There will be no safety subgroup analyses for this study.

10.6 Other Safety Analyses

There will be no other safety analyses for this study.

11.0 Other Analyses

There will be no other safety analyses for this study.

12.0 Interim Analyses

12.1 Data Monitoring Committee

There is no data monitoring committee for this open label study.

13.0 Overall Type-I Error Control

Overall type-I error for Period A will be controlled by testing the co-primary endpoints, followed by the ranked and only secondary endpoint, in a hierarchical order as described in Section [3.1](#) and Section [3.2](#).

Overall type-I error for Period B will be controlled by testing the primary endpoint, followed by the ranked secondary endpoints, in a hierarchical order as described in Section [3.1](#) and Section [3.2](#).

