# 7 STATISTICAL METHODS & DETERMINATION OF SAMPLE SIZE

## 7.1 Statistical and Analytical Plans

---

The statistical methods provided in this protocol will be focused on primary and ranked secondary analyses. Complete and specific details of the statistical analysis will be described in the Statistical Analysis Plan (SAP).

The Primary Analysis for Period A will be conducted after all continuing subjects have completed Week 16 visit and the database is locked. This will be the only and final analysis for the primary and secondary efficacy endpoints for Period A.

The Primary Analysis for Period B will be conducted after all continuing subjects have completed Week 52 visit and the database is locked. This will be the only and final analysis for the primary and secondary efficacy endpoints for Period B.

The final analysis will be conducted upon study completion. The statistical analysis will be described and fully documented in the SAP. All statistical tests will be performed at a two-sided alpha level of 0.05. The statistical analyses will be performed using SAS (SAS Institute Inc., Cary, North Carolina, USA).

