## 7.7 Overall Type I Error Control

---

Overall type-I error for Period A will be controlled by testing the co-primary endpoints, followed by the ranked and only secondary endpoint, in a hierarchical order as described in Section 3.2 and Section 3.3.

Overall type-I error for Period B will be controlled by testing the primary endpoint, followed by the ranked secondary endpoints, in a hierarchical order as described in Section 3.2 and Section 3.3.

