The primary efficacy objective in Period B is to demonstrate a higher rate of PASI 90 after switching the treatment at Week 16 from APR to RZB for 36 weeks (APR/RZB) when compared to continuing with APR (APR/APR) based on the Intent to Treat Population in Period B for Week 16 APR-PASI75NRs (ITT_B_NR), which consists of subjects randomized to APR at Baseline, failed to achieve PASI 75 at Week 16 and are re-randomized.

The hypothesis corresponding to the primary objective and endpoint in Period B is:

- The proportion of APR-PASI75NR subjects achieving PASI 90 in the APR/RZB group is greater than that in the APR/APR group at Week 52, among the ITT_B_NR Population.

The estimand corresponding to the primary efficacy objective in Period B is defined as follows:

- Difference in the percentage of subjects achieving PASI 90 at Week 52 without satisfying the rescue criteria or receiving the rescue medication, and without receiving alternative PsO treatment regardless of premature discontinuation of study drug, in the APR/RZB group in comparison to the APR/APR group among the ITT_B_NR population

Key Secondary Efficacy Objective:

The key secondary efficacy objective in Period A is to demonstrate higher efficacy of treatment with RZB when compared to APR with respect to the ranked and only secondary endpoint in Period A among the ITT_A Population, as specified in Section 3.2 below.

The hypothesis corresponding to the ranked and only secondary efficacy objective and endpoint in Period A is:

- The proportion of subjects achieving PASI 75 in the RZB group is greater than that in the APR group at Week 16, among the ITT_A Population.

The estimand corresponding to the ranked and only secondary efficacy objective in Period A is defined as follows:

- Difference in the percentage of subjects achieving PASI 75 from Baseline at Week 16 without receiving alternative PsO treatment, regardless of premature discontinuation of study drug, in the RZB group in comparison to the APR group among the ITT_A population.

The key secondary efficacy objectives in Period B are to demonstrate higher efficacy of treatment with APR/RZB when compared to APR/APR among the ITT_B_NR Population, with respect to the key secondary endpoints in a ranked order in Period B, as specified in Section 3.2 below.

The hypotheses corresponding to the ranked secondary efficacy objective and endpoints in Period B are:

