2.4 Sample Size Determination

This study plans to enroll a total of $N = 330$ subjects, to be sufficiently powered to detect the treatment difference between risankizumab (RZB) and apremilast (APR) with respect to the co-primary endpoints in Period A, as well as between APR/RZB and APR/APR with respect to the primary endpoint in Period B:

- Assuming that 50% of APR-PASI75NR subjects in the APR/RZB group and 20% of APR-PASI75NR subjects in the APR/APR group will achieve PASI 90 at Week 52 in Period B, the sample size of 120 re-randomized APR-PASI75NR subjects (60 subjects per group) will have more than 90% power to detect the treatment difference between APR/RZB and APR/APR, using a Chi-square test with a 2-sided significance level of 0.05.
- Assuming 55% of subjects initially randomized to APR will be re-randomized at Week 16 under the APR-PASI75NR (as defined by the PASI 75 response at Week 16) stratum, the total sample size for the initial APR group is $120/55\% = 220$. Assuming the treatment difference is at least 40% with respect to the co-primary endpoints of PASI 90 and sPGA of 0 or 1 at Week 16 in Period A, the total sample size of $N = 330$ subjects (RZB: 110, APR: 220) will

also provide more than 90% power to detect the treatment difference between RZB and APR, using a Chi-square test with a 2-sided significance level of 0.05.

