9.0 Efficacy Analyses

9.1 General Considerations

All efficacy analyses will be conducted among the ITT Population in each analysis period. All tests will be 2-sided at an alpha level of 0.05.

The Primary Analysis for Period A will be performed after all ongoing subjects have completed Week 16 and all data pertaining to Period A are cleaned. This will be the only and final analysis for efficacy in Period A.

The Primary Analysis for Period B will be performed after all ongoing subjects have completed Week 52 and all data pertaining to Period B are cleaned. This will be the only and final analysis for efficacy in Period B.

The final analysis will be performed upon study completion.

Categorical Endpoints:

For categorical endpoints, the number and proportion of subjects who achieved the endpoint, as well as the 95% confidence interval (CI) of that proportion, will be provided by each treatment group among all ITT Populations.

In addition, comparisons between treatment groups will be made in the following analyses, with the estimated treatment difference, as well as the corresponding 95% CI and the p-value provided among the following populations:

- ITT_A Population: Comparisons in Period A will be made between RZB and APR using the Cochran-Mantel-Haenszel (CMH) test, adjusting for the actual values of stratification factors at Baseline: Baseline body weight (≤ 100 kg, > 100 kg) and prior exposure to any systemic and/or biologic treatment for psoriasis ($0, \geq 1$). In case of any stratum with zero subject in either treatment group, no stratification factor will be controlled.
- ITT_B_NR Population: Comparisons in Period B will be made between APR/RZB and APR/APR using the chi-square test.

- ITT_B_Combined Population: Comparisons in Period B will be made between APR/RZB and APR/APR using the CMH test, adjusting for the actual values of the stratification factor of re-randomization: PASI 75 response status at Week 16 (Yes/No). In case of any stratum with zero subject in either treatment group, no stratification factor will be controlled.

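### Does testing Period A and Period B each at two-sided 0.05 leave a type I error claim in the plan unmet?

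*SAP*

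**What the plan says.** SAP 13.0 has two sentences on multiplicity. The first begins "Overall type-I error for Period A will be controlled by testing the co-primary endpoints" and continues to the single ranked secondary endpoint of that period. The second reads "Overall type-I error for Period B will be controlled by testing the primary endpoint, followed by the ranked secondary endpoints, in a hierarchical order". Protocol 7.7 has the same pair; its second sentence begins "Overall type-I error for Period B will be controlled by testing the primary endpoint, followed by the ranked secondary endpoints".

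SAP 9.1 sets the level: "All tests will be 2-sided at an alpha level of 0.05". SAP 2.4 justifies one enrolment of 330 for the Period A comparison "as well as between APR/RZB and APR/APR with respect to the primary endpoint in Period B", and applies two-sided 0.05 to each comparison in turn. Protocol 7.1 says of the Week 16 analysis: "This will be the only and final analysis for the primary and secondary efficacy endpoints for Period A". It has a parallel sentence for Period B at Week 52. SAP 2.1 gives Period B its own hypothesis: "The proportion of APR-PASI75NR subjects achieving PASI 90 in the APR/RZB group is greater than that in the APR/APR group at Week 52".

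Neither document splits alpha between the periods, makes Period B testing depend on Period A, claims control across both periods, or uses the word family.

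**The concern.** The section title speaks of overall type I error control. Both periods have an objective labelled primary, and one sample size serves both. A reader who stops at the title could conclude that the chance of any false primary claim from this trial is held at 5%. Two unlinked hierarchies at full 0.05 do not give that. They also allow a Period B claim to stand when Period A has failed. If control across the whole trial had been promised, the real error rate could be nearly double the stated one, and the wording of the trial's conclusions would be affected.

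**Working it through.** **1. Inputs.** Two-sided 0.05 for every test (SAP 9.1, Protocol 7.1). Period B: 50% against 20%, 60 per group. Period A: 110 against 220, a difference of at least 40 points, apremilast rate not given (all SAP 2.4).

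**2. The plan's own figures, at 0.05 per period.**
- Period B: pooled rate 0.35, so SE under the null = √(2 × 0.35 × 0.65 / 60) = 0.0871. SE under the alternative = √((0.25 + 0.16) / 60) = 0.0827. z = (0.30 − 1.96 × 0.0871) / 0.0827 = 1.56, so power is 94.1% (94.2% by exact enumeration). The plan says more than 90%.
- Period A: over assumed apremilast rates from 0.1% to 59.9%, power at 40 points is always above 99.9%. The plan says more than 90%.
- Enrolment: the SAP starts from "Assuming 55% of subjects initially randomized to APR will be re-randomized at Week 16 under the APR-PASI75NR". Then 120 / 0.55 = 218.2, taken as 220, and 220 + 110 = 330. The shared total arises because one enrolment must supply enough apremilast non-responders; it implies nothing about shared alpha.

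**3. Is the control that is claimed delivered?** In each fixed sequence, a false claim requires rejecting the first true null reached, and that test is at 0.05. For the co-primaries, taken in the usual sense that both must succeed, a false joint claim requires rejecting at least one true null at 0.05. So the error is at most 5% in Period A and at most 5% in Period B, as the two sentences say.

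**4. What would the error be if both primary claims were one family?**
- Two-sided: 1 − 0.95² = 0.0975 under independence; 0.05 + 0.05 = 0.10 as a general bound.
- In the hypothesised direction: 1 − 0.975² = 0.0494, to be compared with 0.025.
- Independence is reasonable because of the fresh re-randomisation. A simulation of 200,000 trials with both nulls true gave 4.9% for Period A, 5.1% for Period B, 9.7% for either, and a correlation between rejections of 0.004. It assumed a 20% PASI 90 rate throughout and one endpoint standing for the co-primary pair.
- The 9.75% ceiling needs one co-primary null, the other almost certain to succeed, and a null Period B. With both co-primaries null, the error is 5.2% to 7.8% two-sided and 2.6% to 4.0% directional, for assumed correlations of 0 to 0.9 between their tests.

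**5. What would linking the periods cost?**
- Equal split, 0.025 each: Period B z = (0.30 − 2.241 × 0.0871) / 0.0827 = 1.27, so power is 89.8% (90.3% exact), below or barely at the planned 90%.
- Gating Period B on the co-primaries alone: 94.1% at the planned 40 points.
- Gating on all Period A steps, including Week 16 PASI 75, for which the plan gives no difference: take assumed apremilast rates of 30% (co-primaries) and 45% (PASI 75), and let correlation between steps run from none to full. At 20 points, power runs from 0.943² × 0.935 × 0.941 = 78.2% to 0.935 × 0.941 = 88.0%. At 15 points, it runs from 0.765² × 0.732 × 0.941 = 40.3% to 0.732 × 0.941 = 68.9%.

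**The case for a change.** The best case for the concern is that the text leaves the reader to infer. The heading is general, both objectives are called primary, and nowhere is it presented as a choice that Period B can succeed after Period A fails. One sentence declaring two families would settle the matter at no cost in patients or power.

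Part of this stands. The plan contains no such declaration, and the 9.75% is right on its own premise. A sentence of that kind would do no harm.

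The inference asked of the reader is small, though. In both documents the word overall is followed at once by the period to which it applies, and each sentence then lists the endpoints of that period only. The rest of the plan agrees. Switching is introduced as an additional aim with its own primary objective. Period B is tested in re-randomised apremilast PASI 75 non-responders, Period A in all randomised subjects. Each period has its own final analysis and its own power statement at 0.05. That a Period B claim does not depend on Period A follows directly from two unconnected hierarchies.

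A single sequence across both periods is a legitimate alternative, but a trade-off. It removes any Period B claim when a Period A step fails, and its power cost is material if Period A differences are well below plan. Reasonable statisticians would differ on whether that is worth having.

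**Conclusion.** The concern does not hold. The plan claims 5% control within each period and delivers it; it claims nothing across the two. The 9.75% (4.94% directional, against 2.5%) describes a family that the plan does not define. It is a ceiling under near-independence and an unusual combination of true and false nulls. What is left is an unstated label: writing it down would alter no test, alpha level, power figure or conclusion. This rests on reading each sentence as limited to the period it names, and on the co-primaries both being required. A reader who wants 5% across both primary claims should know that the trial does not offer it, but nothing in the documents says that it does.

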14.0 Version History

Table 3. SAP Version History Summary

Version	Date	Summary
1.0	28 July 2021	Original version
2.0	05 May 2022	
 • Changed Area of safety interest (ASI) to Safety Topics of Interest (STI) to be aligned with the wording of PSSAP. • Changed liver function criteria in Section 10.3 to be aligned with PSSAP. • Changed 'Malignant Tumours' to 'Malignancies' in Appendix B to be consistent with the wording in PSSAP.
3.0	26 February 2023	
 • Changed 'Phase 3b' to 'Phase 4' in the title and Section 1.0 to be consistent with the protocol. • Added Primary Analysis for Period B in Section 9.1. • Added adjusting variables visit and treatment by visit interaction in Mixed-effect Model Repeat Measurement (MMRM) in Section 9.2.2 to be consistent with Section 9.1. • Changed 'cutoff for Period A' to 'cutoff date for Period B' in Section 6.0 and Section 10.2.4. • Added '[and cutoff date during the Primary Analysis for Period B + 1 day]' to Rescue RZB duration in Section 6.0. • CMQ codes were revised for MedDRA 25.1 in Appendix B.

Appendix A. Protocol Deviations

The number and percentage of subjects who reported at least one of the following protocol deviation categories will be provided.

- Subject entered into the study even though s/he did not satisfy entry criteria.
- Subject developed withdrawal criteria during the study and was not withdrawn.
- Subject received wrong treatment or incorrect dose of study.
- Subject took prohibited concomitant medication.

Appendix B. Definition of Safety Topics of Interest

Safety Topics of Interest (STI) will be identified using the following search criteria:

Safety Topics of Interest	Search Criteria	
MACE	Adjudicated terms will be identified as described in PSSAP Table 4a using CECAT and CETERM from the CE SDTM dataset.	
Extended MACE	Adjudicated terms will be identified as described in PSSAP Table 4a (for MACE +) using CECAT and CETERM from the CE SDTM dataset.	
Serious Infections	Serious AEs in the Infections and Infestations SOC	
Active Tuberculosis	Active Tuberculosis CMQ (code 10000002)	
Opportunistic Infections excluding tuberculosis and herpes zoster	Opportunistic infection excluding tuberculosis and herpes zoster CMQ (code 10000105)	
Injection Site Reactions	Narrow	Injection site reaction CMQ (code 10000091)
Malignancies	Narrow	Malignant tumours (SMQ 20000194)
Non-melanoma Skin Cancer (NMSC)	Broad	Skin malignant tumours (SMQ 20000204) excluding terms identified by the Melanoma CMQ (code 10000100)
Malignant Tumours excluding NMSC	'Malignant Tumours excluding NMSC' is identified by the 'Malignant Tumours' search excluding terms identified by the 'Non-melanoma skin cancer (NMSC)' search.	
Hypersensitivity	Narrow	Hypersensitivity (SMQ 20000214)
Serious hypersensitivity reactions	Narrow	Serious AEs in the Hypersensitivity (SMQ 20000214)
Adjudicated Anaphylactic Reaction*	Adjudicated terms will be identified using SDTM data (e.g., CE and PR domains).	
Hepatic Events	Broad	Hepatic failure, fibrosis and cirrhosis and other liver damage-related conditions (SMQ 20000013)
	Broad	Hepatitis, non-infectious (SMQ 20000010)
	Broad	Cholestasis and jaundice of hepatic origin (SMQ 20000009)
	Broad	Liver related investigations, signs and symptoms (SMQ 20000008)
	Narrow	Liver-related coagulation and bleeding disturbances (SMQ 20000015)

* Events will be identified for adjudication by Anaphylactic Reaction SMQ Broad search as specified in the RISA AAC Charter.

Appendix C. Potentially Clinically Important Criteria for Safety Endpoints

The criteria for Potentially Clinically Important (PCI) laboratory findings are described in Table C-1 and Table C-2, and the PCI criteria for vital sign findings are described in Table C-3.

Table C-1. Criteria for Potentially Clinically Important Hematology Values

Hematology Variables	Units	Definition of Potentially Clinically Important Current (Version 4) CTCAE Grade 3 or Greater
		Very Low
Hemoglobin	g/dL	< 8.0
Platelets count	10 ⁹ /L	< 50.0
WBC count	10 ⁹ /L	< 2.0
Neutrophils	10 ⁹ /L	< 1.0
Lymphocytes	10 ⁹ /L	< 0.5

Note: A post-baseline value must be more extreme than the baseline value to be considered a potentially clinically important finding.

Table C-2. Criteria for Potentially Clinically Important Chemistry Values

Chemistry Variables	Units	Definition of Potentially Clinically Important Current (Version 4) NCI CTCAE Grade 3 or Greater	
		Very Low	Very High
TBL	mcmol/L		$> 3.0 \times \text{ULN}$
ALP	U/L		$> 5.0 \times \text{ULN}$
SGOT/AST	U/L		$> 5.0 \times \text{ULN}$
SGPT/ALT	U/L		$> 5.0 \times \text{ULN}$
Albumin	g/L	< 20	
Glucose	mmol/L	< 2.2	> 13.9
Triglycerides	mmol/L		> 5.7
Creatinine	mcmol/L		$> 3.0 \times \text{ULN}$ ($> 3.0 \times \text{BL}$)
Sodium	mmol/L	< 130	> 155
Potassium	mmol/L	< 3.0	> 6.0
Calcium	mmol/L	< 1.75	> 3.1
CPK	U/L		$> 5.0 \times \text{ULN}$
Total Cholesterol	mmol/L		> 10.34
GGT			$> 5.0 \times \text{ULN}$

Note: A post-baseline value must be more extreme than the baseline value to be considered a potentially clinically important finding.

Table C-3. Criteria for Potentially Clinically Important Vital Sign Values

Vital Signs Variables	Criterion	Definition of Potentially Clinically Important
Systolic Blood Pressure (mmHg)	Low	Value ≤ 90 mmHg and decrease ≥ 20 mmHg from Baseline
	High	Value ≥ 160 mmHg and increase ≥ 20 mmHg from Baseline
Diastolic Blood Pressure (mmHg)	Low	Value ≤ 50 mmHg and decrease ≥ 10 mmHg from Baseline
	High	Value ≥ 100 mmHg and increase ≥ 10 mmHg from Baseline

Appendix D. Non-Responder Imputation Incorporating Multiple Imputation to Handle Missing Data Due to COVID-19 Pandemic for Dichotomized Outcome Variables

